## 16.5 Data & Safety Monitoring

16.51 The principal investigator(s) and the study statistician will review the study at least twice a year to identify accrual, adverse event, and any endpoint problems that might be developing. The Mayo Clinic Cancer Center (MCCC) Data Safety Monitoring Board (DSMB) is responsible for reviewing accrual and safety data for this trial at least twice a year, based on reports provided by the MCCC Statistical Office.

16.52 Adverse Event Stopping Rules:

The stopping rules specified below are based on the knowledge available at study development. We note that the rules may be adjusted in the event of either (1) the study re-opening to accrual or (2) at any time during the conduct of the trial and in consideration of newly acquired information regarding the adverse event profile of the treatments under investigation. The study team may choose to suspend accrual because of unexpected adverse event profiles that have not crossed the specified rules below.

**Phase I (Includes all dose levels in phase I):**

By the nature of the “cohorts of three” phase I study design, toxicity (i.e., adverse events that are possibly, probably or definitely related to study treatment) stopping rules are in place for each dose level. Specifically, if 2 or more dose-limiting toxicities (DLTs) are observed during Cycle 2 at any given dose level, accrual to that dose level will be stopped, and patients will be accrued to the next lower dose level until a maximum of 6 patients are treated at the lower level. Note that a DLT that affects dose escalation is only that which is observed in the second cycle of treatment. However, all cycles will be reviewed and the study team will determine whether the dose level needs to be adjusted for future patients if  $\geq 1$  in the first 3 patients OR  $\geq 2$  in the first 6 patients experience a Grade 4 or higher adverse event at least possibly related to treatment over all cycles at any given dose level.

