### Schema

**Phase I Only: Prior to discussing protocol entry with the patient, call the MCCC Registration Office [contact]) for dose level and to insure that a place on the protocol is open to the patient.**

\*Unless adequate tissue is available from biopsy obtained  $\leq$ 90 days prior to registration (see Section 17.0)

\*\*Retreatment (Second Course Phase): Patients who stop pembrolizumab and binimetinib with SD or better may be eligible for up to one year of additional pembrolizumab and binimetinib therapy if they progress after stopping study treatment. This retreatment is termed the Second Course Phase of this study and is only available if the study remains open and the patient meets the requirements as outlined in section 7.5.

Cycle 1 = 14 days

Cycle length for Cycle 2 onward = 21 days

Generic name: pembrolizumab, MK-3475 Brand name(s): Keytruda™ Mayo Abbreviation: MK3475 Availability: Mayo Clinic Pharmacy	Generic name: binimetinib, MEK162 Brand name(s): Mayo Abbreviation: MEK162 Availability: Mayo Clinic Pharmacy
---	--

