## 7.411 Treatment by a local medical doctor is not allowed.

## 7.412 Three patients will be treated at each dose level and observed for a minimum of 21 days after start of pembrolizumab, to assess toxicities, before new patients are treated. Doses will not be escalated in any individual patient. Decisions on when and how to enroll patients at each dose level are described in Section 16.42.

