## 7.413 Investigators are to contact the Study Chair as soon as any dose-limiting toxicity (DLT) occurs.

## 7.42 Definitions of DLT

## 7.421 For this protocol, DLT will be defined as follows for Cycle 2 only:

CTCAE SOC/AE*	Definition (CTCAE Grade)
Blood and lymphatic system disorders	Grade 4
• Febrile neutropenia	
Eye disorders	≥Grade 3
• Blurred vision	
• Flashing lights	
• Floaters	
Eye disorders	Grade 2 lasting >14 consecutive days confirmed by ophthalmic examination Or Grade 3
• Retinopathy	
Eye disorders	Any grade confirmed by ophthalmic examination
• Retinal vascular disorder	

CTCAE SOC/AE*	Definition (CTCAE Grade)
Eye disorders 
 
• Eye disorders, Other specify
 
	Any visual event $\geq$ Grade 3 confirmed by ophthalmic examination
Investigations 
 
• Alanine aminotransferase increased
 
 OR 
 
• Aspartate aminotransferase increased
 
	$\geq$ Grade 3
Investigations 
 
• Blood bilirubin increased
 
	$\geq$ Grade 3
Investigations 
 
• CPK increased
 
	$\geq$ Grade 3 associated with an increase in creatinine $\geq$ 1.5 times patient's baseline (screening) creatinine level
Investigations 
 
• Creatinine increased
 
	$\geq$ Grade 3
Investigations 
 
• Ejection fraction decreased
 
	$\geq$ Grade 3 Or Absolute decrease of LVEF $>$ 10% compared to Baseline and is below the institution's LLN
Investigations 
 
• Electrocardiogram QT corrected interval prolonged
 
	$\geq$ Grade 3 on at least two separate ECGs
Investigations 
 
• Neutrophil count decreased
 
	Grade 4 lasting $>$ 7 consecutive days
Investigations 
 
• Platelet count decreased
 
	Grade 3 with signs of clinically significant bleeding Or Grade 4
Gastrointestinal disorders 
 
• Diarrhea
 
	$\geq$ Grade 3 for $\geq$ 48 hours despite optimal anti-diarrheal therapy Or Grade 4
Gastrointestinal disorders 
 
• Nausea
 
• Vomiting
 
	Grade 3 for $\geq$ 48 hours despite optimal anti-emetic therapy Or Grade 4

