General disorders and administration site conditions 
 
• Fatigue
 
	Grade 3 lasting $>$ 14 consecutive days
Skin and subcutaneous tissue disorders 
 
• Rash maculo-papular
 
• Palmar-plantar erythrodysesthesia syndrome
 
• Photosensitivity
 
	Grade 3 lasting $>$ 14 consecutive days despite maximal skin toxicity treatment per local practice Or Grade 4
Vascular disorders 
 
• Hypertension
 
	Grade 3 lasting $>$ 14 consecutive days Or Grade 4
Other events**	Any $\geq$ Grade 3

\*Adverse event at least possibly related to the study medication.

\*\* Lymphocyte count decreased  $\geq$ Grade 3 (unless clinically significant) and Grade 3 alopecia will not be considered a DLT

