16.42 MTD Determination

The phase I portion of this study will utilize a standard cohort of three design. The dose levels to which patients will be assigned in sequential cohorts are described in Section 7.51. The first cohort of three patients will be treated at dose level 0. Decisions on when and how to dose escalate are described below.

16.421 Three patients will be treated at a given dose level combination and observed for one cycle of the combination (Cycle 2) from start of treatment to assess toxicity.

16.422 If DLT is not seen in any of the 3 patients, 3 new patients will be accrued and treated at the next higher dose level. If DLT is seen in 2 or 3 of 3 patients treated at a given dose level, then the next 3 patients will be treated at the next lower dose level, if only 3 patients were enrolled and treated at this lower dose level.

16.423 If DLT is seen in 1 of 3 patients treated at a given dose level, up to 3 additional patients will be enrolled and treated at the same dose level. If DLT is seen in at least one of these additional three patients ( $\geq 2$  of 6), the MTD will have been exceeded and further accrual will cease to this cohort. If dose-limiting toxicity (DLT) is not seen in any of the three additional patients, 3 new patients will be accrued and treated at the next higher dose level.

16.424 After enrolling 6 patients on a specific dose level, if DLT is observed in at least 2 of 6 patients, then the MTD will have been exceeded and defined as the previous dose unless only 3 patients were treated at the lower dose level. In that case, 3 additional patients will be treated at this lower dose level such that a total of 6 patients are treated at the MTD to more fully assess the toxicities associated with the MTD.

16.426 If a patient fails to complete the first combined cycle (Cycle 2) of therapy for reasons other than dose-limiting toxicity defined adverse events, the patient will be regarded as uninformative in regard to the primary study goal (i.e. MTD determination) and will be replaced.

16.427 Operating Characteristics for standard cohort of 3 design: The following table gives the probability of dose escalation at a single dose level as a function of the true probability of DLT at that level using the cohorts of 3 design described above.

True Rate of DLT (%)	Probability of Dose Escalation
10	0.91
20	0.71
30	0.49
40	0.31
50	0.17

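### Read literally, the Cycle 2 rule leaves duration-based DLTs that start after day 7 uncounted; other sections permit counting them, and no section holds the cohort decision for an open event

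*Combined protocol and SAP*

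**What the plan says.** The Schema sets "Cycle length for Cycle 2 onward = 21 days". Section 7.421 opens its table with "For this protocol, DLT will be defined as follows for Cycle 2 only". Four rows of that table require persistence beyond 14 days:

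- Retinopathy: "Grade 2 lasting >14 consecutive days confirmed by ophthalmic examination", or Grade 3 without a duration.
- Fatigue: Grade 3 for more than 14 consecutive days, with no other trigger in the row.
- Maculo-papular rash, palmar-plantar erythrodysesthesia and photosensitivity: Grade 3 for more than "14 consecutive days despite maximal skin toxicity treatment per local practice", or Grade 4.
- Hypertension: Grade 3 for more than 14 consecutive days, or Grade 4.

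A fifth row counts Grade 4 neutropenia only after more than 7 consecutive days.

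On timing, Section 16.421 has each cohort "observed for one cycle of the combination (Cycle 2) from start of treatment to assess toxicity". The Phase I part of Section 16.52 adds: "Note that a DLT that affects dose escalation is only that which is observed in the second cycle of treatment". Two sections are looser. Section 7.412 has patients "observed for a minimum of 21 days after start of pembrolizumab, to assess toxicities, before new patients are treated", which is a floor and not a ceiling. Section 16.41 considers adverse events that occur in Cycle 2, which can be read as events that begin there.

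**The concern.** A criterion that takes at least 15 days to satisfy sits inside a window of 21 days. If the DLT itself must be observed in the window, most onset days cannot produce one. The patient is then scored DLT-free and the next patients may be entered while the event is still running. In a 3+3 design one event among six patients can change the decision, and the level retained goes into Phase II, where patients treated at the recommended dose also enter the response analysis (Section 16.112).

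The affected events are not remote. Section 15.17 lists fatigue and hypertension as very common with binimetinib and maculo-papular rash as common; Section 15.27 lists fatigue as very common with pembrolizumab. Neither list gives Grade 3 rates.

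**Working it through.** **Inputs.** Cycle length from the Schema; durations from Section 7.421; the 3+3 rule from Sections 16.422 to 16.424; operating characteristics from Section 16.427; the limit of one third from Section 16.41. Two further quantities are assumptions: f, the share of true DLTs that qualify only through the 14-day rows, and m, the share of those with onset too late to qualify by day 21.

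**1. The plan's own table.** The probability of passing a level is (1−p)³ + 3p(1−p)² × (1−p)³. For p = 0.10, 0.20, 0.30, 0.40 and 0.50 this gives 0.906, 0.709, 0.494, 0.309 and 0.172. All five agree with Section 16.427 (0.91, 0.71, 0.49, 0.31, 0.17).

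**2. Day count.** More than 14 consecutive days means at least 15. With onset on day d, the days available by day 21 number 21 − d + 1, and 21 − d + 1 ≥ 15 gives d ≤ 7. So 14 of 21 onset days (67%) cannot yield a DLT under the literal rule. For neutropenia, at least 8 days are needed, so d ≤ 14 and 7 of 21 onset days (33%) are lost. The 3-day administrative window in Section 7.14 could make Cycle 2 last 18 or 24 days, which moves the last scorable onset for the 14-day rows to day 4 or day 10.

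**3. Does another rule catch these events?**
- The all-cycles review in Section 16.52 is triggered only by Grade 4 or higher. It can pick up late Grade 4 neutropenia but not the Grade 2 or 3 events in the four main rows.
- No section says how an event still open at the end of Cycle 2 is classified, or that the cohort decision waits for it.
- For retinopathy, the first scheduled on-treatment eye examination is Cycle 3 Day 1 ± 7 days (Section 4.1, footnote 7). The earliest is about Cycle 2 day 22 − 7 = 15, so a finding first made there cannot be documented for more than 14 days inside Cycle 2.
- Section 16.426 replaces a patient who fails to complete Cycle 2 for reasons other than DLT-defined events, whereas Section 13.7 replaces only for reasons other than toxicity. Under the former, a patient stopped by a toxicity that has not yet met its duration could leave the count.

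**4. Size.** The counted rate is q = p(1 − f·m). Level 0 is both the starting and the highest level, and six patients are to be treated at the MTD. The probability of at most 1 DLT in 6, (1−q)⁶ + 6q(1−q)⁵, is therefore shown beside the pass probability. The true rate is set at 40%, above the protocol's limit of one third.

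| f | m | Counted rate | 3+3 pass | At most 1 in 6 |
|---|---|---|---|---|
| any | 0 (all counted) | 40.0% | 0.309 | 0.233 |
| 10% | 0.33 | 38.7% | 0.331 | 0.255 |
| 25% | 0.67 (uniform onset) | 33.3% | 0.428 | 0.351 |
| 50% | 0.90 | 22.0% | 0.665 | 0.606 |

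For the third row, q = 0.40 × (1 − 0.25 × 2/3) = 1/3. The pass probability is (2/3)³ + 3(1/3)(2/3)⁵ = 0.296 + 0.132 = 0.428. At most 1 in 6 is (2/3)⁶ + 6(1/3)(2/3)⁵ = 0.088 + 0.263 = 0.351.

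**The case against.** The best reply is that the plan does not exclude late events outright. Section 16.41 can be read as counting by onset, and Section 7.412 sets only a minimum observation time. Section 8.1 requires adverse events to be followed until they stabilise or resolve, so the data on an open event would exist. A pembrolizumab hold for a Grade 3 event under Table 8.31 could delay Cycle 3, and the documents do not say that Cycle 2 then closes on day 21. Section 16.52 also lets the team adjust the rules or suspend accrual at any time.

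Much of this stands. A reader might infer that late events can never be scored; the documents do not support that, because two sections leave room to score them. But the looser wording conflicts with Sections 7.421, 16.421 and 16.52, the powers in Section 16.52 are discretionary, and none of these provisions settles how an open event is classified.

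Three limits on scope also stand.
- A reader might infer that rash in general is affected. Acneiform rash has no row of its own and at Grade 3 falls under the other-events row, which has no duration requirement. Grade 4 rash, Grade 4 hypertension and Grade 3 retinopathy also count without one.
- A reader might infer escalation to too high a dose. No level lies above level 0, so the effect is only to keep level 0 or -1 too often.
- Uniform onset over Cycle 2 ignores the 14-day binimetinib run-in, after which some events may already be present. This is one reason to show small values of m.

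**Conclusion.** The point holds as a conflict on the Phase I primary endpoint, with an undercount of DLTs under the more explicit of the two readings. The day count follows from the documents alone, and so does the direction: the 3+3 pass probability falls as the counted rate rises, so each missed DLT favours keeping the dose.

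The size does not follow from the documents. At a true DLT rate of 40%, a 25% duration-only share with uniform onset and long-lasting events raises the pass probability from 0.31 to 0.43, and the probability of at most 1 DLT in 6 from 0.23 to 0.35. With a 10% share and one third of onsets too late, the pass probability moves only from 0.31 to 0.33. A reader might infer a large and established bias in the MTD; without data on how many DLTs qualify by duration alone, that is not supported. What is supported is that the same late event could be scored differently by two investigators, in a design where one event can decide the level.

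**What to change.** Reconcile Sections 7.412, 7.421, 16.41, 16.421 and 16.52 so that they state one rule:

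- An event present in Cycle 2 counts as a DLT if it meets its existing duration criterion, even when that happens after day 21. This covers events with onset in Cycle 2, and events carried over from the run-in that meet their criterion in Cycle 2.
- An open event that could still qualify is followed until it resolves or meets the criterion.
- The cohort decision and entry of the next patients wait for that result.

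The rule should not be by onset in Cycle 2 alone. That would drop an event that starts in the run-in and passes its criterion during Cycle 2, which the present wording of Section 16.52 can count. All grades, durations and doses stay as they are. Sections 16.426 and 13.7 should be reconciled in the same amendment.

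The cost is wording and an occasional wait. In the worst case an event starts on day 21 and meets the 15-day requirement on day 35, a delay of 35 − 21 = 14 days, or about that if visits shift. It arises only in cohorts with an open qualifying event and needs no extra patients.

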**Phase II (includes all phase II patients including phase I patients treated at the MTD):**

Accrual will be temporarily suspended to this study if at any time we observe events considered at least possibly related to study treatment (i.e. an adverse event with attribute specified as “possible,” “probable,” or “definite”) that satisfy either of the following:

- If 3 or more patients in the first 9 treated patients experience a Grade 4 or higher adverse event at least possibly related to treatment.
- If after the first 9 patients have been treated, 25% of all patients experience a Grade 4 or higher adverse event at least possibly related to treatment.

We note that we will review Grade 4 and 5 adverse events deemed “unrelated” or “unlikely to be related”, to verify their attribution and to monitor the emergence of a previously unrecognized treatment-related adverse events.

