##### 16.112 Phase II

The primary endpoint in the phase II portion is confirmed objective response rate (ORR) by RECIST criteria with pembrolizumab and binimetinib.

We will utilize Simon's Two-Stage Optimal Design to test the null hypothesis that this two-drug combination has an ORR of at most 15% versus the alternative hypothesis that it has an ORR of at least 35%. Patients in the phase I part who are treated with the recommended dose of phase II and are evaluable for response will be included in the phase II analysis. The first stage will require 9 evaluable patients. With this design, if  $\leq 1$  of the first 9 patients has objective response (i.e. CR or PR), the study will be closed since there is sufficient evidence that the therapy is not promising. Otherwise, an additional 14 patients will be enrolled. In total, if  $> 5$  patients of 23 patients have objective response, this combination will be considered promising. This design has 80% power while controlling the type I error at 10%. Under the null hypothesis (when the true objective response rate is 15%), this design has a 60% chance of stopping the trial early. A minimum of 9 and a maximum of 23 evaluable patients are required to evaluate the primary endpoint. To account for cases that are ineligible or non-evaluable, we will accrue an additional 3 patients for a maximum accrual of 26 patients in this phase. The secondary endpoints in part II include objective response rate by irRECIST, progression free survival, and overall survival.

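### The Phase II accrual-suspension rule has no trigger of its own for a treatment-related death, so two related deaths in the first 9 patients do not require a pause

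*Combined protocol and SAP*

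**What the plan says.** The Phase II part of section 16.52 has two triggers. The first is "If 3 or more patients in the first 9 treated patients experience a Grade 4 or higher adverse event" rated at least possibly related. The second begins "If after the first 9 patients have been treated, 25% of all patients experience a Grade 4 or higher adverse event", with the same attribution. Both are applied continuously: "Accrual will be temporarily suspended to this study if at any time we observe events considered at least possibly related to study treatment" meeting either condition. The count "includes all phase II patients including phase I patients treated at the MTD".

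The rule's closing note on Grade 4 and 5 events covers only those rated unrelated or unlikely to be related.

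Three other provisions bear on a related death:

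- **Discretion (16.52).** "The study team may choose to suspend accrual because of unexpected adverse event profiles that have not crossed the specified rules below". The same paragraph lets the rules be adjusted during the trial.
- **Reporting (10.52).** Any death within 30 days of the last dose, and any later death with at least possible attribution, needs an expedited report within 24 hours. No accrual step is attached.
- **Phase I (16.52).** Over all cycles, the team decides whether a dose level needs adjusting for future patients if at least 1 of the first 3, or at least 2 "in the first 6 patients experience a Grade 4 or higher adverse event at least possibly related to treatment". Two dose-limiting toxicities in Cycle 2 stop accrual to that level.

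Under 16.51 the DSMB reviews accrual and safety at least twice a year.

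**The concern.** A rule that counts Grade 4 or higher gives a related death the same weight as a related Grade 4 laboratory value. Elsewhere the protocol separates the two. Section 10.31 exempts Grade 4 lymphocyte, neutrophil and platelet decreases from expedited reporting when they do not lead to hospitalization. The dose-limiting toxicity table in 7.42 does not count lymphopenia of Grade 3 or higher unless it is clinically significant. Deaths get a 24-hour report. In the Phase II rule the distinction disappears: three related Grade 4 lymphopenias in the first 9 patients force a suspension, and two related deaths do not.

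This is a single-arm trial of a combination that, according to section 1.5, no trial was testing in breast cancer when the protocol was written. At 10-12 patients a year (16.2), about 5-6 could enroll between two half-yearly DSMB reviews. What is at stake is whether a related death must be reviewed before more patients enroll, or whether that is left to judgment.

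**Working it through.** **Inputs from the documents.** First trigger: 3 of the first 9. Later trigger: 25% of all patients, read here as at least 25%. Stage 1 size: "The first stage will require 9 evaluable patients" (16.112). Maximum evaluable 23 and maximum accrual 26 (16.112).

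**The plan's own figures.** The suspension rule has no stated operating characteristics to reproduce. The Simon design that supplies the 9 and the 23 does reproduce:

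- Early stopping at a 15% response rate: 0.85^9 + 9 × 0.15 × 0.85^8 = 0.2316 + 0.3679 = 0.5995 (stated 60%).
- Type I error: 0.0990 (stated 10%).
- Power at 35%: 0.8037 (stated 80%).

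**Boundary.** The smallest count that forces suspension is 3 up to n = 9, then the smallest k with k/n ≥ 0.25:

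| Patients treated | Count that suspends |
|---|---|
| 9-12 | 3 |
| 13-16 | 4 |
| 17-20 | 5 |
| 21-24 | 6 |
| 25-26 | 7 |

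Reading the rule as more than 25% changes the count only at n = 12, 16, 20 and 24.

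**Two deaths in the first 9.** 2 < 3, and 2/9 = 22.2% < 25%. No ordering crosses. If nothing further happens, 2/10 = 20% and the share keeps falling.

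**Larger counts.** 5/23 = 21.7% and 6/26 = 23.1% are both below 25%. Because the rule runs continuously, the running count must also have stayed below every earlier boundary. Enumerating all orders:

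- 5 events in 23: 9,385 of 33,649 orders never cross (27.9%).
- 6 events in 26: 36,806 of 230,230 orders never cross (16.0%).

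**Probability illustration.** The documents give no rate for related deaths or for related Grade 4 events, so both are assumed and varied. Each patient has a related death with probability d, a related Grade 4 event without death with probability g, or neither, with probability 1 − d − g. An exact patient-by-patient recursion applies the boundary above over 26 patients. Each outcome is taken as known before the next patient is treated.

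| d | g | Rule suspends | 2+ related deaths, no mandatory suspension | 3+ related deaths, no mandatory suspension |
|---|---|---|---|---|
| 10% | 0% | 13% | 62% | 36% |
| 10% | 10% | 56% | 26% | 12% |
| 10% | 15% | 75% | 13% | 5% |
| 5% | 0% | 2% | 35% | 12% |
| 5% | 10% | 33% | 18% | 5% |
| 5% | 15% | 56% | 10% | 2% |

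**The case against.** **Deaths do not go unnoticed.** They are reported within 24 hours. Unexpected serious suspected reactions go to the FDA and all investigators (10.0), and 10.42 adds the IRB. Twice-yearly DSMB review is a minimum. Section 10.2 treats an event as unexpected when its observed severity is not listed, so a related death could well fall under the discretionary clause. All of this stands, and a reader who inferred that related deaths would pass unexamined would be going beyond the documents. But none of these provisions requires accrual to pause.

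**Phase I already acts on some of these patterns.** Six patients are to be treated at the MTD (16.41), and they count in Phase II. If they are the first 6 of the 9, the Phase I review condition is met by every placement of two deaths except those with none in the first 3 and at most one among patients 4-6. There are C(9,2) = 36 placements and C(6,2) − C(3,2) = 15 − 3 = 12 exceptions, so 24 of 36 (67%) would prompt the review. A related death in Cycle 2 would also be a dose-limiting toxicity under the catch-all row in 7.42. This stands for Phase I patients. A death in a patient who enters directly into Phase II meets only the pooled rule.

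**Larger counts.** A reader might infer that 5 related deaths in 23 patients never suspend accrual. The documents do not support that, because the rule applies continuously and about 72% of orders would have crossed earlier. Only the case of 2 in the first 9 holds in every order.

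**The 62% figure is the extreme.** It needs a 10% related-death rate and no related Grade 4 events at all. Any background of Grade 4 events brings suspension sooner, as the table shows. When that happens, however, the pause depends on the other toxicities as well as the deaths.

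**A trigger at one death is a choice.** It will sometimes pause a trial whose true related-death rate is low. That is correct, and the cost is given under the fix.

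**Conclusion.** The point holds as a gap in a monitoring rule that is cheap to close; it does not invalidate the trial. As written, the Phase II rule requires no suspension after two related deaths in the first 9 patients, in any order, and no other provision makes a pause mandatory for patients who enter in Phase II.

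How often this would matter cannot be fixed from the documents. Across the assumed rates (related deaths 5% or 10%, related Grade 4 events 0-15%), two or more related deaths without mandatory suspension occur in 10% to 62% of 26-patient trials. The figures take 25% as at least 25%, assume immediate knowledge of outcomes, and leave out discretionary suspension and the Phase I rules. They describe what the Phase II rule compels, not what a careful team would do.

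**What to change.** Add a third bullet to the Phase II rule in 16.52, for example: *Accrual pauses after any Grade 5 event rated possibly, probably or definitely related to study treatment, pending prompt review by the study team and the DSMB.* Leave the two Grade 4 thresholds unchanged. The Simon boundaries, the sample size and the treatment of enrolled patients are not affected.

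The cost is a short accrual pause for each related death, in a trial expected to enroll 10-12 patients a year. The chance of at least one pause in 26 patients is 1 − (1 − p)^26 for a true related-death rate p. At assumed rates of 1% and 2% that is 23% and 41%; at 5% and 10% it is 74% and 94%. The low-rate figures are the price of the change, and prompt review keeps each pause short.
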